The study is a single-blinded randomised controlled trial. Participants are older adults, aged 67 or older, receiving home help services, who are able to walk with or without walking aids, who have experienced at least one fall during the last twelve months and who have a Mini Mental State Examination of 23 or above. The intervention group receives a programme, based on the Otago Exercise Programme, lasting twelve weeks including home visits and motivational telephone calls. The control group receives usual care. The primary outcome is health-related quality of life (SF-36). Secondary outcomes are leg strength, balance, walking speed, walking habits, activities of daily living, nutritional status and falls efficacy. All measurements are performed at baseline, following intervention at three months and at six months' follow-up. Sample size, based on the primary outcome, is set to 150 participants randomised into the two arms, including an estimated 15-20% drop out. Participants are recruited from six municipalities in Norway.

Discussion:

This trial will generate new knowledge on the effects of an exercise falls prevention programme among older fallers receiving home help services. This knowledge will be useful for clinicians, for health managers in the primary health care service and for policy makers.

Trial registration: ClinicalTrials.gov. NCT02374307. First registration, 16/02/2015.

Keywords: Falls prevention, Home help services, Elderly, Quality of life, Older adults, Exercise, Balance, Preventative care

Background

Older adults and health-related quality of life

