Six municipalities in the Oslo region have agreed to take part in the research project. Participants are recruited through consultants in the municipalities coordinating and providing home help services. The researcher visits the municipalities on a regular basis to conduct the recruitment. Additionally, health workers in the municipalities are informed about the criteria to participate and will alert about eligible participants. Eligible participants will be contacted by the researcher by telephone and asked to consent to being sent information about the study. After a week, they will be contacted again to see if they consent orally to participate. Before baseline testing, the participants must provide a written informed consent. Figure 1 presents the planned flow of participants in the study.

Inclusion and exclusion criteria

Inclusion criteria are: Individuals who 1) are 67 or older, 2) receive home help services 3) have experienced at least one fall during the last twelve months, 4) are able to walk with or without a walking aid and 5) understand Norwegian. Exclusion criteria are: 1) medical contraindications to exercise, 2) life expectancy below one year, 3) a score below 23 on the Mini Mental State Examination (MMSE) and 4) currently participating in other falls prevention programmes or trials.

Randomisation

The participants are randomly assigned at a 1:1 ratio to the intervention group and the control group. A computer-generated, permuted block randomisation scheme is used to allocate the participants. Following randomisation, the participants receive information by telephone on which group they are allocated to. See flow chart in Figure 1.

In order to optimize the rigor of the RCT and to minimize bias, a number of methodological factors have been incorporated into the design of the study. The study participants will be randomly allocated to the groups via concealed allocation, as inadequately concealed allocation has been associated with bias in RCTs [43]. Due to the nature of the intervention, it is not possible to blind the participants or the treating therapists to the allocated groups. However, all assessors are blinded to the allocated groups. In further attempts to reduce bias, data will be analysed on an intention-to-treat basis. This preserves the randomisation process and imitate the real-life situation where the possibility exists that not all participants receive the prescribed treatment.

Study intervention

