Falls efficacy is assessed using the Falls Efficacy Scale International (FES-I). This scale has shown good reliability and validity assessing concerns about falling in older adults, and is recommended for clinical trials and practise [66, 67]. It is a self-reported questionnaire, containing 16 items on different activities of daily living. Level of concern is measured on a four-point scale ranging from 1, which is not at all concerned, to 4 which is very concerned [68].

Adherence to the programme is documented through an activity diary completed by the participants and a form checked by the physiotherapists during home visits and calls. Additionally, the participants have a falls calendar where they report adverse events. Adverse events are registered in the following four categories: falls, cardiovascular events, musculoskeletal injuries and health care utilization and will be documented as “due to the intervention” or “not due to the intervention” [69].

Sample size estimation

The sample size is estimated from the primary outcome, HRQOL (SF-36). A treatment difference of 10 points between the two groups in one of the domains in SF-36 is regarded to be of statistical and clinical significance. The associated standard deviation is assumed to be around 20 points. This implies a moderate effect size [70], which can be expected as previous OEP studies have shown substantial effects on physical outcomes [45]. Moreover, a similar Norwegian study, which included older adults performing exercise following discharge from hospital, estimated the required sample size identically [71]. Given a power of 80% and level $\alpha=0.05$, we aim at including 150 participants, allowing for a 15-20% dropout, to detect a difference of 10 points between groups (see Figure 1).

Statistical procedures

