Statistical analysis is performed using SPSS or a similar statistical package. Descriptive data are reported for variables of interest. The data will be analysed following the intention to treat principle [72]. Prospective differences in primary and secondary outcomes and baseline characteristics between the intervention group and the control group will be assessed by t-tests for continuous and normal distributed variables and with non-parametric tests for categorical variables. Multiple linear regression modelling are used to control for confounding of between-group differences [73]. Hypotheses about mediating factors are tested through correlations, multiple regressions and bootstrapping methods exploring the correlations and explained variance of the chosen mediating factors and the changes in QOL [74]. Bootstrapping is a non-parametric method and is considered favourable with dichotomous variables (group 1 and 2) and small samples ($n < 250$) [74].

Discussion

The main purpose of the study is to evaluate the impact of OEP on HRQOL in older adults receiving home help services. We anticipate that the intervention described in this protocol will have a positive impact on the HRQOL. The tailored intervention will have a potential to promote evidence-based decision-making and empower older people receiving home help services to remain to a greater extent in charge of their own lives. We rely on a systematic approach, which corresponds with the guidance on developing and evaluating RCTs [75]. Only a few studies have included HRQOL when measuring the effect of a falls prevention programme, and most of these studies include it as a secondary outcome [21, 76]. Outcomes examining HRQOL are selected based on literature identifying a standard set of measurements in falls prevention programmes [77, 78]. SF-36 is chosen due to its good validity, reliability and responsiveness when assessing older adults [79]. This outcome is detailed and broad, but it might be putting a burden on the participants due to its length and sensitive questions. Nevertheless, estimating HRQOL is important to determine whether the effect of a falls prevention programme is significant enough to achieve clinical relevant changes and thus to justify the implementation.

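### The 150 participants cover about 15% dropout, not the stated 15-20%: at 20% dropout power is about 77.5%, and 160 would be needed for 80%

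*Combined protocol and SAP*

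**What the plan says.** Under Methods, Sample size estimation, the protocol bases the number on the SF-36. The target is "A treatment difference of 10 points between the two groups in one of the domains in SF-36". On variability it says: "The associated standard deviation is assumed to be around 20 points". Power is set at 80% and alpha at 0.05, and the conclusion is that "we aim at including 150 participants, allowing for a 15-20% dropout, to detect a difference of 10 points between groups".

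The Methods part of the abstract makes the same claim: the sample size "is set to 150 participants randomised into the two arms, including an estimated 15-20% drop out". Both places therefore present the dropout allowance as already contained in the 150.

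Two other sections supply the rest of the calculation. Randomisation: "The participants are randomly assigned at a 1:1 ratio to the intervention group and the control group". Statistical procedures: group differences are "assessed by t-tests for continuous and normal distributed variables". The text does not give the number of completers required, whether the test is one- or two-sided, or how the number was inflated for dropout.

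**The concern.** A dropout allowance given as a range has to hold at the upper end of that range. A difference of 10 with an SD of 20 is a standardised effect of 0.5, which needs about 126 to 128 completers. If 20% of 150 are lost, 120 remain, which is fewer than required.

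This is the only power statement for the primary outcome, and readers will use it to interpret a null or borderline result. The section on the intervention describes the participants as frail and expects them to keep to the programme less well than more independent older people. Losses near the upper end of the range therefore cannot be set aside as unlikely.

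**Working it through.** **Inputs.** Difference 10 points, SD 20, power 80%, alpha 0.05, dropout 15-20% and 150 randomised (Sample size estimation); 1:1 allocation (Randomisation); two-sample t-test (Statistical procedures). Two-sided testing is assumed, because the text does not say.

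**Completers required.**
- Normal approximation: n per arm = 2 × (1.960 + 0.842)² × (20/10)² = 62.8, so 63 per arm and 126 in total.
- Two-sample t-test, standardised effect 0.5: 63.8, so 64 per arm and 128 in total.

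**Reproducing the 150.** The enrolment needed is completers / (1 − dropout).

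| Dropout | From 126 (normal) | From 128 (t-test) |
|---|---|---|
| 15% | 126/0.85 = 148.2, so 149 | 128/0.85 = 150.6, so 151 |
| 20% | 126/0.80 = 157.5, so 158 | 128/0.80 = 160 |

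The figure of 150 is reproduced at 15% dropout. At 20% it is 8 to 10 participants short.

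**Power with 150 randomised.**

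| Dropout | Remaining | t-test | Normal approximation |
|---|---|---|---|
| 15% | 127.5 | 80.0% | 80.6% |
| 17.5% | 123.75 | 78.8% | 79.4% |
| 20% | 120 | 77.5% | 78.2% |

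For the 20% row by the normal approximation, the standard error is 20 × √(2/60) = 3.65. Then 10/3.65 − 1.96 = 0.78, which corresponds to 78.2%.

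**Largest dropout that 150 can absorb.** 1 − 128/150 = 14.7% by t-test, or 1 − 126/150 = 16.0% by the normal approximation. The midpoint of the stated range already falls below 80% on both.

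**Detectable difference.** With 60 per arm, the difference detectable with 80% power by t-test is 10.3 points.

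**One-sided check.** A one-sided test needs 50 to 51 per arm, 100 to 102 in total. Inflating 102 gives 102/0.85 = 120 to 102/0.80 = 127.5, so 120 to 128 enrolled. That does not lead to 150, whereas two-sided testing at 15% dropout does.

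**Possible origin.** Multiplying completers by (1 + dropout) gives 126 × 1.15 = 144.9 to 126 × 1.20 = 151.2, or 128 × 1.15 = 147.2 to 128 × 1.20 = 153.6. That would bring 150 close to the whole stated range, so this common slip is a possible explanation. It is not established, since correct division at 15% gives the same figure.

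**The case against.** The strongest objection is that the gap is smaller than the precision of the inputs. The SD is given only approximately. With 60 per arm, t-test power returns to 80% at an SD of about 19.4 and is 81.6% at an SD of 19. By the normal approximation the loss at 20% dropout is only 1.8 percentage points. This stands as a point about size, but it cuts both ways: at an SD of 21 power is 73.5%, so there is no hidden slack.

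Second, the count of 120 treats every dropout as lost to the primary comparison. Outcomes are measured at three and six months, the protocol does not say at which visit the 15-20% applies, and the analysis is by intention to treat. Someone lost after three months could still contribute a three-month value. That is a fair caution. But no missing-data method is described that would keep dropouts in the analysis, so complete-case loss is the natural reading.

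Third, a baseline-adjusted analysis could recover the loss. With 60 per arm, a correlation between baseline and follow-up of 0.25 gives about 80.1% power, 0.3 gives 81.3% and 0.5 gives 88.0%. These correlations are assumptions; the protocol gives none. The sample size section does not rely on adjustment, and the regression under Statistical procedures is described as controlling confounding, without naming baseline SF-36 as a covariate. Adjustment is available as a remedy but does not support the sentence as written.

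Finally, Figure 1, to which the sample size sentence refers, could not be seen for this review and may show planned numbers. The inputs and the dropout claim are complete in the text, so it would not change the arithmetic.

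**Conclusion.** The concern holds. The base calculation is sound and 150 is right for about 15% dropout, but the claim that it covers 15-20% is not correct. At 20% dropout power is 77.5% by the planned t-test (78.2% by the normal approximation), and 80% would require 160 participants (158).

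The shortfall is about 2.5 percentage points at worst and matters less than uncertainty in the SD. It is an overstated power claim, not a flaw in the design. The result assumes two-sided alpha 0.05, an SD of exactly 20, a single pre-named SF-36 domain, an unadjusted comparison, and no outcome data from dropouts.

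**What to change.** Restate the sentence under Sample size estimation along these lines: 150 participants give 80% power to detect a 10-point difference (SD 20, two-sided alpha 0.05) with up to about 15% dropout, and about 77-78% power at 20% dropout. Change the abstract to match.

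Alternatively, base the power statement on an analysis adjusted for baseline SF-36, name that analysis under Statistical procedures, and state the assumed correlation. A value of at least about 0.3 keeps power above 80% at 20% dropout.

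The cost of the restatement is one sentence in each of two places, and a power figure slightly less favourable than the one now stated. No extra enrolment is needed.

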HRQOL is the primary outcome measured by the Short Form 36 Health Survey (SF-36) [52]. This is a generic and validated questionnaire which, translated into Norwegian, is conducted as an interview [53]. The 36 items in SF-36 are grouped into eight health status scales: physical functioning, role limitations due to physical problems and due to emotional problems, bodily pain, general health perception, vitality, social functioning and mental health [52].

Secondary outcome variables

In addition to the SF36, the EQ-5D (1990 EuroQOL EQ-5D) is reported. The EQ-5D is a generic and validated questionnaire [54-57]. It describes five dimensions of HRQOL (mobility, self-care, usual activities, pain/discomfort, anxiety/depression), each of which can take one of five responses at five levels of severity (no problems/slight problems/moderate problems/severe problems/severe problems/extreme problems).

Physical function includes measures of balance, gait speed, muscle strength as well as activities of daily living. The Bergs Balance Scale is a 14-item scale, which is applied to assess static and dynamic balance in older adults [58]. Gait speed is assessed by measuring usual walking speed over four meters [59] and muscle strength is measured by the 30 seconds sit to stand test [60]. Instrumental ADL is recorded using the Norwegian Version of the Lawton IADL scale, which is a valid and reliable measure of a person's self-reported ability to perform complex activities of daily living [61].

Physical activity is measured using the “Walking habits questionnaire”, a valid questionnaire for walking habits and physical activity for frailer older people [62]. This questionnaire assesses general behaviour of walking, regarding how often and for how long. The following questions are asked: “Do you take a daily walk?” (yes/no) or “If you do not take a daily walk how many times per week do you take a walk?” (never/almost never/1-2 days/3-4 days/ almost daily) and “How long does you walk generally last? (0-15 mins/15-30mins/30-60mins/ 1h-2h/>2h)”. Walking time in minutes per week is calculated by taking the lowest level of days multiplied by lowest level of minutes for each response alternative [62].

Nutritional status is measured using the Mini Nutritional Assessment (MNA- elderly, Société des Produits Nestlé, S.A., Vevey, Switzerland) form. The first screening part of six questions is used which includes measurement of weight and height for calculation of BMI [63-65].

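### Intention to treat is promised with 15-20% dropout expected, but no missing-data method is stated and adjustment for baseline SF-36 is not assured; this may cost precision and allows bias if HRQOL-related loss differs between arms

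*Combined protocol and SAP*

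**What the plan says.** Intention to treat is promised twice. Under Randomisation, "data will be analysed on an intention-to-treat basis"; under Statistical procedures, "The data will be analysed following the intention to treat principle". The reason given under Randomisation is that some participants will not receive the treatment assigned to them. That concerns adherence, not absent outcome data.

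Under Sample size estimation, "we aim at including 150 participants, allowing for a 15-20% dropout". The target is "A treatment difference of 10 points between the two groups in one of the domains in SF-36", and "The associated standard deviation is assumed to be around 20 points"; whether that is the SD at one visit or of change is not said.

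For the comparison itself, "Prospective differences in primary and secondary outcomes and baseline characteristics between the intervention group and the control group will be assessed by t-tests" (non-parametric tests for categorical variables). It is not stated whether follow-up scores or changes from baseline are tested. In addition, "Multiple linear regression modelling are used to control for confounding of between-group differences", with no list of covariates.

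SF-36 is measured at baseline, 3 months and 6 months (Outcome measures). SPIRIT checklist item 20c covers both the analysis population and missing-data methods and points to pages 6-7. The text does give the population. No section gives a missing-data method.

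**The concern.** Intention to treat fixes who belongs to each arm. It does not say what to do when a member of that arm has no score. At 15-20% dropout, about 22 to 30 of 150 participants are affected (0.15 x 150 = 22.5; 0.20 x 150 = 30). A t-test without imputation leaves them out, so the analysis promised and the test named do not meet unless a missing-data assumption is stated.

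Two things are at stake. First, if baseline SF-36 is not adjusted for, precision is lost: a follow-up-score t-test ignores baseline, and a change-score t-test uses it less efficiently than regression does. Second, if the link between HRQOL and dropout differs between arms, in rate or in mechanism, a t-test on those who remain can be biased in either direction.

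**Working it through.** **Inputs from the documents.** Difference 10 points, SD 20, power 80%, alpha 0.05 (taken as two-sided), 1:1 allocation, 150 randomised, 15-20% dropout.

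**Assumptions, not in the documents.** Baseline-to-follow-up correlation r, the split of dropout by arm, and the strength of the link between HRQOL and dropout.

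**The plan's own figure.** n per arm = 2(1.96 + 0.84)² x 20² / 10², which rounds up to 63, or 126 in total. Dividing by 1 - d gives 126/0.85 = 149, 126/0.84 = 150 and 126/0.80 = 158. So 150 reproduces near the 15% end.

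**Precision.** At 20% loss, 75 x 0.80 = 60 per arm remain. If 20 is the SD at one visit, the effective SD is 20 for follow-up scores, 20√(2(1 - r)) for change and 20√(1 - r²) with baseline adjustment. If 20 is the SD of change, the change t-test has SD 20 and the adjusted analysis 20√((1 + r)/2). Power by noncentral t:

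| r | Follow-up t (SD 20 at one visit) | Change t (SD 20 at one visit) | Adjusted (SD 20 at one visit) | Change t (SD 20 is of change) | Adjusted (SD 20 is of change) |
|---|---|---|---|---|---|
| 0.4 | 77.5% | 70% | 84% | 77.5% | 90% |
| 0.6 | 77.5% | 86% | 92% | 77.5% | 86% |
| 0.8 | 77.5% | 99.0% | 99.5% | 77.5% | 82% |

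At r = 0.3 with SD 20 at one visit, adjustment gives 81%. At 15% loss (75 x 0.85 = 63.75 per arm) the follow-up t-test has 80.0%.

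**Bias, basic arithmetic.** Within an arm, the completer mean is off by the dropout share times the completer-minus-dropout gap. For example, 20% loss with a 10-point gap in one arm only gives 0.20 x 10 = 2.0 points. Equal shares and equal gaps in both arms cancel to 0.

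**Bias, simulation.** 75 per arm, SD 20, no true effect, r = 0.6, logistic dropout with log-odds slope per SD lower score, 20,000 replicates. Unless stated, loss is 20% in the exercise arm and 15% in control. Mean estimates in points, exercise minus control:

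| Loss depends on | Slopes (exercise, control) | Follow-up t | Change t | Adjusted |
|---|---|---|---|---|
| Baseline score | 1.0, 1.0 | +0.50 | -0.36 | -0.02 |
| Baseline score | 0.7, 0.7 | +0.35 | -0.26 | -0.01 |
| Baseline score | 1.0, 0.7 | +0.90 | -0.60 | +0.01 |
| Baseline score | 0.7, 1.0 | -0.02 | -0.01 | -0.02 |
| Baseline score, 17.5% loss in each arm | 1.0, 1.0 | -0.01 | -0.01 | -0.01 |
| Baseline score, exercise arm only (extreme) | 1.0, none | +2.13 | -1.39 | +0.01 |
| Unobserved outcome | 1.0, 1.0 | +0.80 | +0.32 | +0.53 |
| Unobserved outcome | 0.7, 0.7 | +0.62 | +0.25 | +0.40 |
| Unobserved outcome | 1.0, 0.7 | +1.48 | +0.63 | +1.00 |
| Unobserved outcome | 0.7, 1.0 | -0.08 | -0.05 | -0.06 |
| Unobserved outcome, exercise arm only (extreme) | 1.0, none | +3.48 | +1.40 | +2.27 |

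Reversing the rates (15% exercise, 20% control, slopes 1.0 and 1.0, baseline-driven) reverses the signs: -0.50 and +0.29 for the two t-tests. With baseline-driven loss in both arms, t-test type I error was 5.0-5.6%. In the one-arm baseline-driven extreme (slopes 0.7 to 1.0) it was 7-9% on follow-up scores.

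**Two follow-up visits.** Half the loss falls before 3 months and depends on baseline; half falls later and depends on the observed 3-month score (10,000 replicates, all pairwise correlations 0.6). At 6 months, baseline-only adjustment leaves 0.11-0.21 points with loss in both arms and about 0.5 in the one-arm extremes. A mixed model on all three visits leaves 0.00-0.02.

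**The case against.** The strongest reply is that regression is already planned and may well include baseline SF-36, in which case no precision is lost. That stands. A reader might infer that the plan is certain to lose precision, but the documents leave adjustment open; they do not rule it out. The gain also depends on a correlation the documents do not give. At r = 0.3 it is 77.5% against 81%, and at r = 0.8 a change-score t-test already reaches 99.0%.

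A reader might also infer that dropout will bias the result, perhaps in favour of exercise. The documents do not support this. They give one overall dropout rate, not a rate by arm or a cause. The Study intervention section lists poor health, fear of falling and depression as barriers to adherence, and only one arm carries the exercise demand. That makes unequal loss plausible but gives no rate or direction. In the runs above, unequal rates and unequal slopes can cancel to about 0.

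The remedy is not better in every case. If loss follows the unobserved outcome, baseline adjustment leaves bias and does worse than a change-score t-test. That too stands, and is why a sensitivity analysis is needed.

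Finally, it would be too strong to call SPIRIT item 20c unmet: the analysis population is stated, and only the missing-data half is absent.

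**Conclusion.** The gap holds as a conditional one, and is worth correcting because it concerns the primary outcome. No missing-data method accompanies the intention-to-treat promise, and baseline adjustment is not assured.

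If baseline is left out, a follow-up-score t-test falls slightly short of 80% power at 20% loss, while adjustment exceeds 80% at every correlation tried (0.3 to 0.8). With low-baseline-HRQOL loss in both arms at 20% versus 15%, t-test bias is about 0 to 0.9 points on follow-up scores and about 0 to 0.6, usually of opposite sign, on change scores. A one-arm extreme gives about 2 points on follow-up scores. The same rate and mechanism in both arms gives 0 when there is no true effect. If loss follows the unobserved outcome in both arms, bias is about 0 to 1.5 (follow-up t), 0 to 0.6 (change t) and 0 to 1.0 (adjusted).

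These are modest against 10 points. They rest on assumed slopes of 0.7 to 1.0, an assumed correlation of 0.6 and an assumed dropout split.

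**What to change.** In Statistical procedures:

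- Make the primary SF-36 comparison the linear regression already planned, in place of the t-test: follow-up score on arm, with the baseline score on the same scale as a named covariate and participants analysed as randomised.
- State that the analysis assumes missing at random.
- Add a delta-adjusted multiple-imputation sensitivity analysis, with shifts applied to each arm separately, for example 5 and 10 points. A shift in one arm moves the estimate by missing share times delta: 0.15 x 5 = 0.75 to 0.20 x 10 = 2.0 points.
- Report dropout and its reasons by arm.

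The regression can leave about 0.1-0.2 points of bias at 6 months (0.5 in one-arm extremes) when later loss depends on the 3-month score. A linear mixed model using the baseline, 3- and 6-month scores removes this under missing at random, and is the preferred option if the team is willing.

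The cost is a few sentences and slightly more analysis of data already collected, with no new visits or measures. The downside is reliance on missing at random, which the sensitivity analysis examines but cannot prove. Which SF-36 scale and visit should be primary is a separate multiplicity question, not raised here.

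### Baseline characteristics are significance-tested between randomised arms and regression then handles confounding with no covariate or selection rule named; a covariate set fixed in advance, including the baseline outcome, would gain power at no cost in patients

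*Combined protocol and SAP*

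**What the plan says.** Three parts of the Methods bear on this point.

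- **Statistical procedures** puts outcomes and baseline variables under the same between-arm tests: "Prospective differences in primary and secondary outcomes and baseline characteristics between the intervention group and the control group will be assessed by t-tests" where variables are continuous and normal, with non-parametric tests for categorical ones. The next sentence adds: "Multiple linear regression modelling are used to control for confounding of between-group differences". No covariate is named here or elsewhere, no rule for choosing covariates is given, and baseline SF-36 is not committed to as one. The SPIRIT checklist (items 20a and 20b) points back to this page and cites no separate analysis plan.
- **Randomisation** states: "The study participants will be randomly allocated to the groups via concealed allocation", with "The participants are randomly assigned at a 1:1 ratio to the intervention group and the control group".
- **Outcome measures** places the baseline assessment before randomisation and has the primary and secondary outcomes measured at baseline as well as at three and six months.

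**The concern.** Because baseline data are collected before a concealed random allocation, the null hypothesis of every baseline test among randomised participants is true by design. A significant result is a chance event, and a non-significant one does not show that a prognostic variable is balanced closely enough to ignore. What makes a covariate worth adjusting for is that it predicts the outcome, and a baseline p-value carries no information on that.

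The language of confounding belongs to observational work. In a randomised trial, adjustment serves to gain precision and to remove chance imbalance in prognostic variables. With no covariates named, the plan forgoes a dependable gain in power from data it already collects. It also leaves room to choose among adjusted models after the results are visible.

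**Working it through.** **Inputs from the documents (Sample size estimation; Randomisation).** The target is "A treatment difference of 10 points between the two groups in one of the domains in SF-36"; "The associated standard deviation is assumed to be around 20 points"; "Given a power of 80% and level $\alpha=0.05$, we aim at including 150 participants", "allowing for a 15-20% dropout"; allocation 1:1. Two-sided testing is my assumption, and it reproduces the plan's N.

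**Assumptions not in the documents.** Baseline-outcome correlation r of 0.3 to 0.7. A count of 19 baseline variables: age, education, MMSE, eight SF-36 scales, and eight secondary measures (EQ-5D, Berg, gait speed, sit-to-stand, IADL, walking habits, MNA, FES-I). The plan's own list of baseline variables is open.

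**1. The plan's sample size.** n per arm = 2 × 20² × (1.960 + 0.842)² / 10² = 62.8, so 63 per arm and 126 in total. Allowing for dropout, 126/0.85 = 148.2 (149) and 126/0.84 = 150. The stated 150 reproduces at about 15-16% dropout; at 20% the same formula gives 158. The calculation assumes no covariate adjustment.

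**2. Chance flags at baseline.** With 19 tests at 0.05, 19 × 0.05 = 0.95 flags are expected. The chance of at least one is 1 − 0.95¹⁹ = 62% if the variables are independent. If they are equally correlated at 0.3 to 0.5, it is about 52% to 41%. With 10 independent variables it is 40%.

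**3. What a non-significant test lets through.** With 75 per arm, the standard error of a baseline difference is 20 × √(2/75) = 3.27. The critical difference is 1.976 × 3.27 = 6.45 points, so a smaller gap is non-significant. The chance of a gap between 3 and 6.45 points is 31% per scale. On average, a baseline gap carries into the unadjusted outcome comparison in proportion to r: 6.45 × 0.3 = 1.9 and 6.45 × 0.7 = 4.5 points.

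**4. Power with and without a prespecified covariate.** At 20% dropout there are 60 per arm, and the standard error is 20 × √(2/60) = 3.65. Adjustment multiplies it by √(1 − r²), and power = Φ(10/SE − 1.96).

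| Analysis | SE | Power, 60 per arm | Power, 63.75 per arm (15% dropout) |
|---|---|---|---|
| Unadjusted | 3.65 | 78.2% | 80.6% |
| Adjusted, r = 0.3 | 3.48 | 81.9% | 84.1% |
| Adjusted, r = 0.5 | 3.16 | 88.5% | 90.3% |
| Adjusted, r = 0.7 | 2.61 | 97.0% | 97.7% |

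**5. An illustrative rule: adjust only if baseline p < 0.05.** This rule is not in the plan; it shows what would follow if baseline p-values were used. Two simulations at 60 per arm were run, for r = 0.3, 0.5 and 0.7.

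- One prognostic covariate, 200,000 trials per scenario. It was selected in about 5% of trials whatever its r. Power was 77.8%, 78.5% and 79.3%, against 81.1%, 87.7% and 96.7% when it was fixed in advance and about 77.5% unadjusted. Type I error was 4.8%, 4.3% and 3.7%, against about 5.0%.
- Nineteen independent baseline variables, one of them prognostic, 4,000 trials per scenario. Power was about 76-78%, and type I error 3.5-4.8%.

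**6. Conditional error.** In the first simulation, when the prognostic covariate's baseline p fell between 0.05 and 0.15, the unadjusted test's type I error was 6.5%, 9.5% and 13.6%. The adjusted analysis stayed at about 5%.

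**The case against.** The strongest reply is that the two sentences in Statistical procedures are separate. A baseline table with p-values alongside covariates chosen on clinical grounds would fit the wording just as well. This stands. A reader might infer that the baseline tests are the plan's screen for covariates, but the text states no screen at all. What it supports is that covariate choice is unspecified and open to baseline p-values.

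A reader might also infer that the false-positive rate is inflated. It is not: even the illustrative rule is slightly conservative overall, and the excess error in step 6 is conditional on a particular imbalance.

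Setting 6.45 points directly against the 10-point target would overstate the matter too, since only the fraction r of a baseline gap reaches the outcome.

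Nor does the plan lose power against its own sample-size basis, which is unadjusted. The shortfall is a gain not taken, and deleting the baseline tests alone would not recover it.

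Finally, with 15-20% dropout the participants analysed may differ between arms for reasons other than chance, so regression adjustment has a legitimate purpose. That also stands, but it favours prognostic covariates chosen in advance and does not make a baseline p-value a sound way to pick them.

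**Conclusion.** The point holds in this limited form. Testing baseline characteristics between the randomised arms is explicit in the plan and uninformative under its own design. The regression that follows has no stated covariates, and baseline SF-36 is not secured as one.

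The consequences are forgone power, bias of roughly 1.9 to 4.5 points when a baseline SF-36 gap lies just under the significance threshold, and freedom to choose covariates after the fact. The power gain available at 60 per arm is from about 77-78% to about 82%, 88% or 97%. The gain and the bias both rest on the assumed r of 0.3 to 0.7. The 41-62% chance of at least one false flag rests on the count of 19 variables and on their correlation.

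This is an improvement that should be made. It is not an error that invalidates the trial: overall type I error is at or below nominal and N = 150 is unaffected.

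**What to change.** 1. Remove baseline characteristics from the sentence on testing, and report them by arm as means (SD) or counts without p-values.
2. Make the primary between-group analysis a linear model with treatment arm and the baseline value of the outcome, plus any other prognostic covariates named before unmasking. Use this set whatever the observed balance.
3. Replace the reference to confounding with that prespecified adjustment, and state that no covariate is added or dropped because of a baseline p-value.

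The cost is a few sentences of analysis-plan wording. The baseline values are already collected, no participants are added, and N = 150 stays as it is. Step 1 alone changes no result; the gain in power comes from step 2.
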